2.4.1.4 Dose delays/interruptions/modifications

The number of subjects who have dose delays/interruptions (for Lutathera only)/modifications, and the reasons, will be summarized separately for each of the study treatment components.

For Lutathera, ‘Was there any delay?’, ‘If administered dose is not full dose’, and ‘Has Lutathera infusion been interrupted?’ fields from the Lutathera treatment eCRF will be used to determine the dose delays/modifications/interruptions, dose reductions, infusion interruptions, respectively. In addition, the reason for dose delays/modifications/interruptions will be presented for the Lutathera arm. The number of cycles delayed, number of infusion interruptions for Lutathera will be summarized descriptively.

For Octreotide LAR, ‘Is there any delay?’, and ‘Different dose, specify’ fields from the Octreotide Long-Acting treatment eCRF will be used to determine the dose delays, and dose modifications, respectively. For both arms, delay/modifications of Octreotide dose will be summarized with reason presented. In addition, the number of cycles delayed for Octreotide will be summarized descriptively.

2.4.2 Prior, concomitant and post therapies

Prior anti-cancer therapy

The number and percentage of patients who received any prior anti-neoplastic medications, prior anti-neoplastic radiotherapy or prior anti-neoplastic surgery will be summarized by treatment arm. Prior anti-neoplastic medications will be summarized by therapy type (e.g., chemotherapy, immunotherapy, hormone therapy, and other). The medication therapy type of any combination therapy will be classified based on the following order: chemotherapy, immunotherapy, hormone therapy, other. In addition, prior anti-neoplastic medications will be further summarized by lowest ATC class, preferred term and treatment. The above analyses will be performed using the FAS.

Post treatment anti-cancer therapy

Anti-neoplastic therapies since discontinuation of study treatment will be listed and summarized by ATC class, preferred term, overall and by treatment group by means of frequency counts and percentages using FAS. Anti-neoplastic cancer surgeries/procedures will also be listed and summarized by overall and treatment group using the FAS.

Post treatment anti-neoplastic therapy will include:

- Medications:
 - Medications which are in the ATC2 class of Antineoplastic agents or
 - Medications which are in the ATC4 class of Various therapeutic radiopharmaceuticals
 - Medications which are in the ATC4 class of Somatostatin and Analogues
- Procedures:

- Any radiotherapies
- Procedures (including surgery) with indication of Underlying disease in Concomitant non-drug therapies and interventions eCRF page

Concomitant medications

All medications taken at the start of screening until the end of the treatment phase /optional treatment extension Phase (Cross-over period)/optional re-treatment phase (re-treatment period), or early termination, are to be recorded. This includes prescription and over-the-counter medications taken during this time frame.

During the Follow-up Phase, concomitant medications must be collected only if administered for related SAEs/AESI and/or for secondary hematological malignancies. In addition, further anti-tumor treatments for GEP-NET administered after progression must be reported until the end of the Follow-up phase. Concomitant therapy include medications (other than study drugs) starting on or after the start date of study treatment or medications starting prior to the start date of study treatment and continuing after the start date of study treatment.

Concomitant medications will be coded using the World Health Organization (WHO) Drug Reference Listing (DRL) dictionary that employs the WHO Anatomical Therapeutic Chemical (ATC) classification system and summarized by lowest ATC class and preferred term using frequency counts and percentages. Surgical and medical procedures will be coded using MedDRA and summarized by SOC and preferred term (PT).

All concomitant therapies will be listed. Any concomitant therapies starting and ending prior to the start of study treatment or starting more than 30 days after the last date of study treatment will be flagged in the listing. The safety set will be used for concomitant medication tables and listings for the randomized period.

2.5 Analysis of the primary objective

The primary objective of the study is to determine whether Lutathera is superior to active comparator in delaying the time-to-first occurrence of progression or death (PFS) as first line treatment.

2.5.1 Primary endpoint

The primary endpoint of the study is progression-free survival (PFS), defined as the time from the date of randomization to the date of the first documented progression or death due to any cause. PFS will be assessed via central review according to RECIST 1.1. The Full Analysis Set will be the primary analysis population and will include all data observed up to the cut-off date.

If a patient has not progressed or died by the analysis cut-off date, PFS will be censored at the date of the last adequate tumor evaluation date before the cut-off date.

PFS events documented after the initiation of new anti-neoplastic therapy (i.e., RECIST 1.1 documented disease progression per central review or death) will be censored for the primary analysis at the last adequate tumor assessment prior to start of the new therapy. A separate

sensitivity analysis will be conducted that considers such events as PFS events for the primary analysis provided central review of tumor assessments continues after initiation of new cancer therapy. Additional details regarding censoring rules and determination of date of last adequate tumor assessment are provided in [Section 2.5.3](#).

Discontinuation due to disease progression (collected on the 'End of Treatment' disposition page) without supporting objective evidence satisfying progression criteria per RECIST 1.1 will not be considered disease progression for PFS derivation. Clinical deterioration will not be considered as a qualifying event for progression in the primary analysis.

2.5.2 Statistical hypothesis, model, and method of analysis

Assuming proportional hazards model for PFS, the null hypothesis will be tested at one-sided 2.5% level of significance:

H_0 (null hypotheses): $\Theta_1 \geq 0$ vs. H_{a1} (alternative hypotheses): $\Theta_1 < 0$, where Θ_1 is the log hazard ratio of PFS in the Lutathera plus Standard Dose octreotide long-acting (30 mg) (investigational) arm vs. High Dose octreotide long-acting (60 mg) (control) arm.

H_0 (null hypothesis): $S_L(t) \leq S_C(t)$ will be tested against the following

H_a (alternative hypothesis): $S_L(t) > S_C(t)$,

where $S_L(t)$ is the survival function of PFS in the Lutathera plus Standard Dose octreotide long-acting (30 mg) (investigational) arm, and $S_C(t)$ is the survival function of PFS in the High Dose octreotide long-acting (60 mg) (control) arm.

The primary efficacy analysis to test this hypothesis and compare the two treatment groups will consist of a stratified log-rank test at an overall one-sided 2.5% level of significance in favor of the Lutathera plus Standard Dose octreotide long-acting (30 mg) arm. The stratification will be based on following randomization stratification factors (histological grade: G2 vs. G3; and tumor origin: pNET vs other origin).

Analyses will be based on the FAS population according to the randomized treatment group and strata assigned at randomization. The PFS distribution will be estimated using the Kaplan-Meier method, and Kaplan-Meier curves, median and associated 95% confidence intervals will be presented for each treatment group. The hazard ratio for PFS will be calculated, along with its 95% confidence interval, from a stratified Cox model using the same stratification factors as for the log-rank test.

In case of few events in some stratum, which may seriously impact the power, the primary analysis will instead be unstratified. More specifically, if any of the four strata counts less than eight PFS events, the primary analysis will be unstratified (Vittinghof and McCullugh, 2007). Both stratified and unstratified analyses will be presented.

More technical details concerning the analysis of PFS follow in [Section 5.4.1](#).

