In accordance with the recently finalized guidance for industry on considerations for the inclusion of adolescent patients in adult oncology clinical trials and the consensus expert opinion presented by the European multi-stakeholder platform ACCELERATE to include adolescents in adult oncology clinical trials when the histology and biologic behavior of the cancer under investigation is the same in, or the molecular target of the drug is relevant to, cancers in both adult and adolescent patients (FDA guidance), this study will include adolescents ≥ 15 years and >40 kg BW. Even though the number of adolescents ≥ 15 years fulfilling the inclusion criteria for this study is very small, the high unmet medical need in this population is justifying their enrollment. It is not

expected that adolescents below the age of 15 years will present with the disease meeting the inclusion criteria for this study.

Due to the radioactive nature of Lutathera and its method of infusion, and similarly to the NETTER-1 trial design, it is not possible to implement a fully double-blinded design for this study, however a central, blinded, real-time IRC (Independent Review Committee) assessment is implemented to ensure an independent evaluation of the tumor response according to RECIST 1.1 criteria.

Randomization will be stratified by Grade (G2 vs G3) and tumor origin (pNET vs other origin), preventing imbalance between treatment groups for known factors that influence prognosis.

For this trial a 2:1 randomization design is chosen to allow patients to have a higher chance of getting the treatment which is anticipated to be more effective. For the same reason and to minimize the possible higher drop-out rate in the control arm, patients will be offered to cross-over to Lutathera after centrally confirmed RECIST progression (or locally confirmed if it occurs after Week 72 post the primary end point analysis).

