2.6.2 Statistical hypothesis, model, and method of analysis

ORR and its 95% confidence interval will be presented by treatment group.

The null hypothesis of the ORR in the investigational arm is less than or equal to the ORR in the control arm will be tested against the one-sided alternative. The statistical hypotheses are:

H_{02} : ORRR \leq ORRC versus H_{A2} : ORRR $>$ ORRC, for a one-sided test

where ORRR is the probability of response in investigational arm and ORRC is the probability of response in control arm.

The Cochran-Mantel-Haenszel chi-square test, stratified by the randomization stratification factors, will be used to compare ORR between the two treatment groups, at the 1-sided 2.5% level of significance. More details concerning the calculation are provided in [Section 5.4.2](#).

The analysis of QoL Time to Deterioration (TTD) will be the same as for PFS, employing log-rank test and Cox regression, see above, and, Appendix for further details.

Assuming proportional hazards model for TTD, the null hypothesis will be tested at one-sided 2.5% level of significance:

H_{01} (null hypotheses): $\Theta_1 \geq 0$ vs. H_{a1} (alternative hypotheses): $\Theta_1 < 0$,

where Θ_1 is the log hazard ratio of TTD in the Lutathera plus Standard Dose octreotide long-acting (30 mg) (investigational) arm vs. High Dose octreotide long-acting (60 mg) (control) arm.

For each domain, a Kaplan-Meier plot will be produced showing time to event by treatment arm. Kaplan-Meier methods will be used to generate a point estimate of the median time to event with corresponding 95% confidence interval (CI).

The stratified log-rank test will be used to compare the time to event in the two groups at the one-sided 2.5% level. The hazard ratios (HR) and corresponding 95% CIs were estimated from a stratified Cox proportional hazards model including randomized treatment as a factor. If too few events occur in any stratum (less than eight), then the main analysis will be unstratified. Both stratified and unstratified analyses will be presented.

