2.13 Interim analysis

There will be no interim analysis with inferential intent. But, at the time of the PFS primary analysis, an estimate of overall survival will be calculated in terms of hazard ratio (point estimate) and 95% confidence interval. Furthermore, a presentation of safety will be prepared including data from the time period up the interim.

3 Sample size calculation

The sample size calculation is based on the primary variable PFS. Assuming a median PFS in the control arm (High Dose octreotide long-acting (60 mg)) of approximately 15 months, it is hypothesized that treatment with Lutathera added to standard dose octreotide long-acting will result in a 50% reduction in the hazard rate (corresponding to an increase in median PFS from 15 months to 30 months).

To ensure 90% power to test the null hypothesis: PFS hazard ratio = 1, versus the specific alternative hypothesis: PFS hazard ratio = 0.50, it is calculated that a total of 99 PFS events need to be observed. This calculation assumes analysis by a one-sided log-rank test at the overall 2.5% level of significance, patients randomized to the two treatment groups in a 2:1 ratio. Assuming that enrolment will continue for approximately 22.2 months at a rate of 10 patients per month and a 15% dropout rate by the time of the final PFS analysis, a total of 222 patients (148 for Lutathera arm and 74 for the control arm) will need to be randomized to observe the targeted 99 PFS events at about 12.8 months after the randomization date of the last patient, i.e., 35 months after the randomization date of the first patient. If the final analysis is performed when the targeted 99 PFS events are observed, the observed hazard ratio will have to be < 0.658 which corresponds to a difference in median PFS of 7.8 months to declare statistical significance.

These calculations were made using the software package East 6.4.

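### One sparse stratum makes the primary PFS test drop both randomization factors; sparse cells should instead be collapsed in a pre-specified order that keeps grade

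*SAP*

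**What the plan says.** SAP 2.5.2 makes the primary test a log-rank stratified by grade (G2, G3) and tumor origin (pNET, other), with a matching stratified Cox model. It then says that few events in a stratum could badly hurt power, so "if any of the four strata counts less than eight PFS events, the primary analysis will be unstratified". It cites a paper whose title concerns events per variable in logistic and Cox regression, and it promises both the stratified and the unstratified result.

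For the four TTD tests, SAP 2.6.2 says: "If too few events occur in any stratum (less than eight), then the main analysis will be unstratified". SAP 2.5.6 and 2.6.6 use a similar fallback for the supplementary Cox models, without a number.

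Protocol 12.4.2 already foresees an unstratified fallback and leaves the handling of strata to the SAP. Protocol 4.1 gives the purpose of stratified randomization as "preventing imbalance between treatment groups for known factors that influence prognosis".

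Other places do not match the fallback:
- The estimands in SAP 1.3.1 and 1.3.3 name only the stratified test.
- SAP 5.4.1 calls the unstratified log-rank a sensitivity analysis.
- SAP 2.5.5 plans an unstratified Cox sensitivity analysis with no exception for the case where the primary analysis is itself unstratified. Protocol 12.4.4 makes that exception.
- For response rate, SAP 5.4.2 answers sparse data with an exact stratified test and does not drop the strata.

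**The concern.** The event count in one cell decides whether the primary test and hazard ratio adjust for grade and origin at all, even if the other three cells are well filled. The two analyses also target different quantities: a hazard ratio within strata, or a marginal one. If the factors are prognostic, as the protocol says, leaving them out pulls the hazard ratio toward 1. It also makes the log-rank test conservative, because randomization was stratified.

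The power argument in the SAP does not fit the test it describes. SAP 5.4.1 computes a rank statistic S_k and its variance in each stratum, and forms Z = ΣS_k / √Σvar(S_k). No parameter is estimated per stratum, so a limit on events per estimated parameter has no direct bearing. A thin stratum adds little to either sum.

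**Working it through.** **1. The plan's own figure (SAP section 3).** Inputs: "one-sided log-rank test at the overall 2.5% level of significance", 90% power, hazard ratio 0.50, 2:1 allocation.
- Events = (1.960 + 1.282)² / [(2/3)(1/3)(ln 0.5)²] = 98.4, rounded up to 99. The stated 99 is reproduced.
- Power at 99 events is 90.2%.
- Critical hazard ratio = exp(−1.960/√(99 × 2/9)) = 0.658, and 15/0.658 − 15 = 7.8 months. Both match.

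This calculation does not mention strata.

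**2. When the rule fires.** Eight events is 8/99 = 8.1% of the total, against an average of 99/4 = 24.75 per stratum. The documents give no stratum shares. If the two factors are independent, the smallest cell holds on average:
- G3 35%, pNET 50%: 0.35 × 0.50 × 222 = 38.9 patients. The rule fired in at most 0.4% of simulated trials.
- G3 10%, pNET 50%: 11.1 patients. It fired in 67% to 99%, depending on prognosis.
- G3 35%, pNET 10%: 7.8 patients. It fired in 94% to 99%.

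**3. Power when it fires.** The simulation used 20,000 to 40,000 trials per scenario, N = 222, 2:1, a cut at the 99th event and a within-stratum hazard ratio of 0.5. Assumed: blocks of 6, exponential PFS, and the shares and prognostic hazard ratios shown. Monte Carlo error of an overall power figure is about √(0.9 × 0.1/20,000) = 0.2 point.

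| G3 / pNET share | Prognostic HR: grade, origin | Fires | Stratified | Unstratified | Difference (points) |
|---|---|---|---|---|---|
| 8% / 50% | 1, 1 | 99.9% | 91.9% | 92.4% | +0.5 |
| 10% / 50% | 1, 1 | 99% | 92.1% | 92.4% | +0.3 |
| 10% / 50% | 2, 1 | 84% | 91.5% | 91.6% | about 0 |
| 10% / 50% | 3, 1.5 | 67% | 91.3% | 90.3% | −1.1 |
| 35% / 10% | 3, 1 | 99% | 91.6% | 88.1% | −3.5 |
| 35% / 8% | 4, 2 | 97% | 91.5% | 84.5% | −7.0 |

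Differences were taken before rounding. Pooling a sparse cell within its grade gave 91% to 92% in every scenario; in the fifth row it gave 91.9%. A separate run of that row (3,000 trials) gave 87.7% under the rule and 92.0% pooled.

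**4. Hazard ratio.** In the last row the average one-step estimate moves from 0.455 stratified to 0.521 unstratified. The one-step stratified estimate reads below the true 0.50 in all scenarios, so only the shift is informative.

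**5. Type I error (one-sided).** Always stratified: 0.026 to 0.030. SAP rule: 0.017 to 0.030.

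**6. Is a grade hazard ratio of 3 to 4 plausible?** Protocol 1.1 quotes five-year survival of 82.0% (Grade 2) and 51.4% (Grade 3) in midgut and hindgut tumors. Under exponential survival the ratio is ln(0.514)/ln(0.820) = 3.35. This is indicative only: it is overall survival, in another population, and this trial takes only G2 tumors with Ki67 of at least 10%, which may narrow the contrast. With grade 3.35 and no origin effect (6,000 trials per mix), power given firing, under the rule against pooling, was:
- G3 35%, pNET 15%: 87.9% against 92.5%; fires in 80%.
- G3 16%, pNET 30%: 89.1% against 91.9%; fires in 43%.
- G3 16%, pNET 50%: 88.7% against 92.1%; fires in 7%, so the overall loss is only 0.2 point.

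**The case against.** The strongest defense is that nothing here threatens validity. The fallback is foreseen in the protocol, fixed numerically in the SAP, driven by event counts that ignore treatment arm, and does not inflate type I error. Any pull of the hazard ratio toward 1 works against the sponsor's claim. Both results will be shown. The sample size does not rely on stratification. All of this stands, and it limits the point to efficiency and clarity.

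A reader might infer that the rule loses power and gains nothing, or that a sparse stratum can do no harm. Neither is supported. In a small stratum, late risk sets may contain one arm only and then contribute nothing. Without prognostic effects the unstratified test is 0.3 to 0.5 point better. The SAP's power reason has the right sign there; at 99 events the size is not serious.

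The losses rest on assumed inputs, and those above about 1 point needed a grade hazard ratio of about 3 or more. Part of the gap is also test size. In the last row of the table, given firing, pooling rejects in 2.85% of null trials and the unstratified test in 1.66%. Setting pooling to exactly 2.5% by normal approximation gives Φ(1.903 + 1.385 − 1.960) = 90.8%, still about 6 points above 84.5%. For the smallest loss, 1.1 points, a similar adjustment could remove much of it.

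Only the title of the cited paper can be seen, so the argument rests on the form of the test and not on that paper's content.

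**Conclusion.** The point holds as one of efficiency and coherence. Discarding both factors because one cell is thin is not justified by the stated reason: retaining all strata costs at most about 0.5 point of power, and only when the factors are not prognostic. If grade has a hazard ratio of 3 to 4, the rule costs about 1 to 7 points when it fires and shifts the hazard ratio toward 1. With weak prognosis the difference is about zero. The chance of firing cannot be narrowed from the documents; it runs from about 0% to 100% with the stratum mix.

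Two stronger readings should be resisted. The documents do not show an underpowered trial: in many mixes the rule rarely fires, or leaves power at or above 90%. Nor do they show a route to a false positive finding or to choosing the analysis after seeing results. The change is worth making because it is nearly free and keeps the analysis aligned with the randomization.

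**What to change.** In SAP 2.5.2, replace the fallback with an order:
1. If any of the four cells has fewer than eight PFS events, pool tumor origin within that grade and keep grade as a stratum.
2. Go unstratified only if a grade still has fewer than eight events after pooling.

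The test and the Cox model should use the same strata. Apply the same rule, counting TTD events, in SAP 2.6.2, and refer to it in 2.5.6 and 2.6.6. Keep the unstratified result as the sensitivity analysis, and exempt it in 2.5.5 when the primary analysis is itself unstratified. State the rule in the estimands (1.3.1, 1.3.3) and in 5.4.1. Record the departure from Protocol 12.4.2 in SAP section 4, which now reads as not applicable.

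The cost is a few sentences before database lock, with no extra data or patients. The downside is up to about 0.5 point of power if neither factor is prognostic.

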2.5.3 Handing of intercurrent events of primary estimand

The analysis will account for different intercurrent events as explained in the following:

- a. Discontinuation of study treatment for any reason before central PFS event: this intercurrent event is ignored (treatment policy strategy).
- b. New anti-neoplastic therapy, including cross-over to Lutathera, before central PFS event: PFS is censored at the date of the last adequate tumor assessment prior to initiation of the new anti-neoplastic therapy (hypothetical strategy).
- c. Re-treatment before central PFS event: PFS is censored at the date of the last adequate tumor assessment prior to re-treatment (hypothetical strategy).

2.5.4 Handling of missing values/censoring/discontinuations

This is an event-driven trial and the primary analysis for PFS will be performed after 99 PFS events have been documented based on central review of tumor assessments.

In the primary analysis, PFS will be censored at the date of the last adequate tumor assessment if no PFS event is observed prior to the analysis cut-off date.

Disease progressions (i.e., central review RECIST 1.1 documented disease progression) or deaths documented after the initiation of new anti-cancer therapy will not be counted as PFS events for the primary analysis.

The date of last adequate tumor assessment is the date of the last tumor assessment with overall response of CR, PR, or SD before an event or a censoring reason occurred. In this case, the last tumor evaluation date at that assessment will be used. If no post-baseline assessments are available (before an event or a censoring reason occurred) then the date of randomization will be used.

In particular, PFS will be censored at the last adequate tumor assessment if one of the following occurs: absence of event; the event occurred after two or more missing tumor assessments.

The term “missing adequate tumor assessment” is defined as a tumor assessment not performed or tumor assessment with overall response of “UNK”. The rule to determine number of missing tumor assessments is based on the time interval between the date of last adequate tumor assessment and the date of an event. If the interval is greater than twice the protocol-specified interval between the tumor assessments and 2 times the protocol-allowed time window around assessments, then the number of missing assessments will be 2 or more.

Note that according to the protocol the first tumor assessment should occur at 16 weeks, then the second tumor assessment should occur 8 weeks later, and then the frequency should be every 12 weeks thereafter. For patients who discontinue from treatment without PD due to central review, tumor assessments should be taken every 12 weeks starting from the last tumor assessment until documented disease progression for central review per RECIST 1.1. Exact time windows to take into account missing assessments for PFS event determination is further discussed in [Section 5.5](#).

Refer to [Table 2.5-1](#) for censoring and event date options and outcomes for primary PFS.

Table 2.5-1 Derivation of primary PFS

Situation	Options	Outcome
A. No baseline assessment, or, No post baseline assessment	Date of randomization	Censored
B. Progression or death at or before next scheduled assessment	Date of progression (or death)	Progressed
C. Progression or death after exactly one missing assessment	Date of progression (or death)	Progressed
D. Progression or death after two or more missing assessments	Date of last adequate assessment prior to missed assessment	Censored
E. No progression (or death)	Date of last adequate assessment	Censored
F. Treatment discontinuation due to 'Disease progression' without documented progression, i.e., clinical progression based on investigator claim	Ignore clinical progression and follow situations above	As per above situations
G. Start of new anticancer therapy, cross-over to or re-treatment with Lutathera prior to protocol defined progression per central review	Primary analysis: Censor patient at last adequate tumor assessment prior to new anti-cancer therapy	Censored
H. Death before first PD assessment	Date of death	Event

In particular, for censoring reason G in [Table 2.5-1](#), new anticancer therapy is defined as one of the following:

- For new anti-cancer medications post-randomization:
 - Medications which are in the ATC2 class of Antineoplastic agents or
 - Medications which are in the ATC4 class of Various therapeutic radiopharmaceuticals

- Class of medications of Somatostatin and Analogues excluding Octreotide and Octreotide Acetate
- For new anti-cancer procedures post randomization:
 - Any radiotherapies
 - Procedures (including surgery) with indication of Underlying disease in Concomitant non-drug therapies and interventions eCRF page

